#### Study Population and Setting

We will recruit Active Clinics from REACHNet and ADVANCE, two of the 10 Clinical Data Research Networks (CDRNs) that comprise PCORnet. We chose these two CDRNs to focus clinic recruitment in safety net clinics and to boost numbers of underserved populations and enhance power to detect heterogeneity of treatment effects. We are targeting clinics that have varied racial/ethnic composition with substantial proportions of Hispanic and Black patients, and patients with lower socioeconomic status. Usual Care Clinics will come from other CDRNs within PCORnet.

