**Sensitivity analyses:** In a sensitivity analysis, we will perform multivariable linear regression analyses to compare clinic-level pre-post differences in our primary and secondary outcomes. The regression models will adjust for health system as well as for whether the clinic was engaged in BP HOME, a concurrently running individual-level randomized trial that will provide home blood pressure monitoring devices to participating patients with a high blood pressure reading in clinic. We will also consider linear mixed models (LMMs) for repeated changes in the summary outcome measures, adjusting for age, sex and race-ethnicity. In particular, for each clinic we will calculate monthly values of the metric  $(t_i - t_0)$ , for follow-up month  $i = 1, \dots, 6$ , within strata jointly defined by age, sex, and race-ethnicity, as well as corresponding within-stratum weights as described above, then estimate the effect of treatment adjusted for stratum, using an LMM that includes treatment assignment, month as categorical, the interaction of these two factors, and stratum. With a view towards model simplification, likelihood ratio testing will be used to determine whether age, sex, and race/ethnicity as additive factors adequately capture the stratification effects. We will: (1) present month-specific treatment effects with 95% confidence intervals (CIs); (2) test for heterogeneity in the monthly treatment effects across months; (3) summarize the treatment effect by the average of the month-specific effects also with a 95% CI, if the test for heterogeneity is not statistically significant ( $P>0.05$ ); and (4) otherwise, use orthogonal contrasts to check for linear and quadratic trends in the monthly effects.

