**Subgroup analysis to test for heterogeneity of treatment effects (HTE):** We will produce clinic-level subgroup-specific analyses limited to subgroups defined by the characteristics listed in Table 3 (with imputation as described above), and test for interactions by intervention group (as well as with Usual Care) and subgroup categories. We hypothesize that the BP Control effect from the Full-Support intervention relative to Self-Guided and Usual Care groups will be smaller in patients who are younger, male, and Black given published BP control difficulties in these patients. We will also specifically test for an interaction between treatment group and enrolling CDRN, given health IT infrastructures may differ by CDRN in ways that can interact with the effectiveness of the interventions. All subgroup analyses will be reported.

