**Table 3. Subgroups for HTE analysis**

Age: 18-44 vs. 45-64 vs. 65+

Race/ethnicity: NH White vs. NH Black vs. NH Asian vs. Hispanic (any race) vs. Other
Sex: Male vs. Female
Enrolling CDRN
HTE – Heterogeneity of treatment effects
NH – Non-Hispanic

**Exploratory Mediation analysis:** As many of our secondary outcomes are presumably process measures in the causal pathway to achieving BP control, we will perform a mediation analysis to understand the degree to which the potential added benefit of the Full Support intervention on BP control is explained by changes in the process measures. We will perform a mediation analysis using nested linear regression models for the effect of randomization assignment (i.e. Full Support vs. Self-Guided) on clinic level pre-post differences in percent control, first omitting, then adding each of our proposed mediators to the base model. The hypothesized process mediators will include pre-post changes in BP measurement accuracy, medication intensification, and average SBP reduction after medication intensification, and repeat visit in 4 weeks after uncontrolled HTN. These analyses will be implemented using the Paramed module in Stata statistical software  to calculate natural direct effect (NDE) of full-support on BP control and the natural indirect effect (NIE) through each mediator. The total causal effect (TCE) is the sum of the NDE and NIE. Dividing each NIE by the TCE will calculate the proportion of the causal effect explained by each mediator.

**Additional exploratory analyses:** We will explore temporal patterns in the effect of randomization assignment using linear mixed models for repeated clinic-level changes since baseline in primary and secondary outcomes assessed at 6, 12, and 18 months. These models will include random effects for clinic, as well as fixed effects for treatment assignment (as a categorical variable), and their interaction. Heterogeneity of treatment effects across time will be tested using a 2 degree-of-freedom chi-square test; in addition, a chi-square test for linear trend will be obtained by comparing the fitted treatment assignment effects at 6 and 18 months.

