**Data source, collection, management, and safety:** Consistent with principles of pragmatic clinical trials, we will use EHR data for patient identification and assessment of intervention implementation and outcomes. Both interventions (and usual care) are consistent with standard of care. Therefore, both the interventions and data collection in this study carry minimal risk to patients. We will leverage the data infrastructure and resources in the PCORnet Common Data Model to collect de-identified, clinic-level aggregate data needed for analysis. Additional details on the PCORnet Common Data Model procedures for data collection and linkage, and data management and safety are described elsewhere.

**Sample size and power:** Preliminary data from “Wave 2” implementation of the M.A.P. Program by AMA in 16 clinics shows average pre-post improvements (without a control group) in BP control of 6.8% (65.6%-->72.4% overall) +/- 4.4% (standard deviation of change in control rate). Assuming negligible change in the Self-Guided arm, standard sample size calculations show that we will have 83% power to detect a difference in differences of 6% in the BP control rate (or 92% power for 7% difference) between Self-Guided and Full-Support arms with 10 clinics randomized to each arm of the study; these results were confirmed using simulations. Power will be higher for comparisons of the Self-Guided and Full-Support groups with the large Usual Care comparison group in PCORnet under similar effect-size

assumptions. For the HTE analysis comparing the difference in differences between the 10 clinics in CDRN 1 (5:5 in each arm) and the 10 clinics in CDRN 2 (5:5 in each arm), we expect to have 80% power to detect an interaction effect (i.e., the difference in the difference in differences) of 12% in the BP control rate. Corresponding minimum detectable interaction effects would be 15%, 13%, and 12% for demographic subgroups comprising 20%, 30%, and 40% of the overall population.

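### Are the 15/13/12-point detectable interactions at odds with the three-category age and five-category race/ethnicity comparisons in Table 3?

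*Combined protocol and SAP*

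**What the plan says.** The sample size and power paragraph takes its SD from a pilot in 16 clinics, "4.4% (standard deviation of change in control rate", and assumes 10 clinics per arm. For the comparison of the two CDRNs (five clinics per arm in each) it gives 80% power for a 12-point interaction. It then adds: "Corresponding minimum detectable interaction effects would be 15%, 13%, and 12% for demographic subgroups comprising 20%, 30%, and 40% of the overall population". It names neither the comparator for such a subgroup nor the test.

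Table 3 lists "Race/ethnicity: NH White vs. NH Black vs. NH Asian vs. Hispanic (any race) vs. Other" and three age bands (18-44, 45-64, 65 and over), together with sex and enrolling CDRN, which have two levels each. The subgroup paragraph of the Analysis Plan will "test for interactions by intervention group (as well as with Usual Care) and subgroup categories". It expects that the Full Support effect "will be smaller in patients who are younger, male, and Black". Study Population and Setting gives, as one reason for choosing these two CDRNs, the wish to "enhance power to detect heterogeneity of treatment effects".

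**The concern.** Sex and CDRN have two levels, so a single contrast describes them fully. Age has three and race/ethnicity five. An overall interaction test would then use 2 or 4 degrees of freedom, and a comparison of two named categories would discard the patients in the others. Both are weaker than comparing one category with all the rest when only that category differs. If the quoted figures are one-against-rest values, a reader could take a null race/ethnicity or age interaction as evidence against differences of 12 to 15 points when the test used had less than 80% power for them. Because power for heterogeneity is a stated reason for the choice of networks, that misreading would matter.

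**Working it through.** **Inputs.** SD of clinic-level change 4.4 points and 10 clinics per arm, from the sample size paragraph. Two-sided 5% is assumed, since the plan states no level for interaction tests and adjusts nothing beyond the three primary tests.

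**1. The plan's figures.** If a subgroup of share p is treated as a share p of the clinics, the one-against-rest interaction has

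SE = 4.4 × √[0.2 × (1/p + 1/(1−p))].

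With 16 residual df, the noncentral t multiplier for 80% power is 2.985.

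| Share p | SE | Detectable effect | Plan |
|---|---|---|---|
| 20% | 4.92 | 14.7 | 15 |
| 30% | 4.29 | 12.8 | 13 |
| 40% | 4.02 | 12.0 | 12 |
| 50% (CDRN) | 3.94 | 11.7 | 12 |

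All four round to the stated values. Two equal-sized categories would instead need about 18.6 points (20% each) or 15.2 (30% each), which do not match. The figures are therefore correct for one subgroup against everyone else.

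**2. Relative loss with more categories.** For a pair, 1/(1−p) is replaced by 1/p2. Since p2 cannot exceed 1−p1, a pair is never more precise than one-against-rest. On the basis of step 1, 20% v 20% needs 2.985 × 6.22 = 18.6 points, and a third v a third needs 2.985 × 4.82 = 14.4 (one-against-rest for a third: 12.5). If the effect is chosen so that one-against-rest has exactly 80% power and only one category differs, the joint test has about 70% for three categories (2 and 36 df). For five it has about 58% with 72 residual df, or 52% with 16. The ordering is not in dispute.

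**3. Power at the stated effect sizes.** The percentages in step 2 come from choosing a new effect in each setting, so they do not give power at 12 to 15 points. For that, clinic size is needed, because every clinic contributes patients to every demographic subgroup and a change shared across a clinic cancels in the interaction. The sampling variance of a clinic's change, using the pilot rates of 65.6% and 72.4% and treating the two periods as independent, is

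10,000 × (0.656 × 0.344 + 0.724 × 0.276)/n = 4254.9/n.

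At n = 220 this is 19.34, against 4.4² = 19.36. The formula in step 1 thus amounts to about 220 patients per clinic with no shared clinic effect. In larger clinics, part of the 4.4 must be shared variation, and the interaction is estimated more precisely.

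For five equal categories with one differing by 15 points, the noncentrality is 15² / [0.2 × (5 × 4254.9/n + s²) × 1.25], where s is an assumed category-specific SD between clinics. Power of the 4-df test (72 residual df):

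| Patients per clinic | s = 0 | s = 2 | s = 6 |
|---|---|---|---|
| 220 | 65% | 63% | 50% |
| 500 | 96% | 94% | 75% |
| 1,000 | over 99% | over 99% | 88% |
| 2,000 | over 99% | over 99% | 94% |

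The 2-df test for three equal categories at 12.5 points, s = 0, has 73%, 98%, over 99% and over 99%. The documents state neither n nor s, so the power of a joint test at the quoted effects may lie well below or well above 80%.

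**4. Dependence on the pattern of effects.** On the basis of step 1 with five equal categories and 72 residual df, effects of 15/0/0/0/0 give the 4-df test 65%, while 15/15/0/0/0 gives 84% and 15/5/−5/5/−5 gives 85%. The loss in step 2 belongs to the one-outlier pattern.

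**The case for a change.** The best case for acting is that the stated power belongs to a contrast the plan never names, while the categories it lists carry no power statement. The phrase about testing by subgroup categories most naturally suggests a joint interaction test, and the plan shows it can be specific: it names a 2-df test for heterogeneity over time but nothing comparable for age or race/ethnicity. The pairwise shortfall is algebraic. With five categories, at least one pair must need 18.6 points or more on the plan's basis, whatever the shares.

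Two things in this stand. The comparator and the test are not written down, and one-against-rest is the most favourable choice when one category differs. What does not follow is a contradiction. The quoted sentence speaks of single subgroups by their share of the population, and the expectations about younger, male and Black patients are one-subgroup statements that such contrasts fit. The listing in Table 3 names levels and does not commit the analysis to pairwise or joint tests. The mixed model under Sensitivity analyses, which has no treatment-by-stratum term, is there for adjustment and does not define the subgroup test.

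**Conclusion.** The concern does not call for a change. The figures of 15, 13 and 12 are correctly calculated for one subgroup against the rest (14.7, 12.8 and 12.0), and no part of the plan ties them to a 2-df, 4-df or pairwise test. A joint or pairwise test would be weaker on the same variance basis if one category differs. Whether its power at 12 to 15 points falls below 80% depends on clinic size and category-specific variation: for the five-category test at 15 points it runs from 50% to over 99% across the settings tried. The claim that the plan is optimistic is therefore not established.

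The gap is one that analysts fill in the ordinary way: one-against-rest contrasts for the directional hypotheses, and an interaction term with the appropriate degrees of freedom where all categories are compared. Reported confidence intervals, rather than planning figures, will show what a null subgroup result can exclude. The subgroup analyses are exploratory, sex and CDRN are two-level comparisons to which the figures apply directly, and the primary test and sample size are untouched. Writing the comparator down would help a reader but would not alter a result or a conclusion. This rests on a two-sided 5% level, 10 clinics per arm, equal category shares in step 3, and the pilot SD and control rates.

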### **Limited program evaluation**

**Objective:** To gain insight into sustainability of the MAP BP program, we will perform a limited program evaluation to examine stakeholder satisfaction with and usability of the online digital guide, and assess barriers and facilitators to implementation and willingness to continue implementation of MAP BP beyond the study period.

**Study procedures:** The limited program evaluation will capture data through two mechanisms: an online survey and a web-based exit interview. Stakeholders will be asked to complete a 10-minute online survey prior to their scheduled exit interview session. For stakeholders who were unable to complete the online survey ahead of time, they will be asked to complete it at the beginning of the virtual interview. Following survey completion, investigators from the University of California San Francisco and the American Heart Association, along with study staff, will conduct 60-minute virtual, web-based exit interview sessions with investigators at each participating site. Each virtual session will include 1:1 semi-structured interviews with individual local stakeholders (i.e. practice change facilitators, site champions, and physician leads) in both study arms. Interviews will be audio-recorded via the web-based platform and transcribed.

**Interview guide:** We will use the COM-B framework and the Technology Acceptance Model (TAM) to inform an interview guide examining the feasibility of continued implementation of both versions of the MAP BP program (self-guided and full-support), barriers and facilitators to implementation, and the usability of the online digital guide component from the perspective of local stakeholders. The capability, opportunity, motivation and behavior (COM-B) model specifies Capability (physical and psychological), Opportunity (social and physical), and Motivation (reflective and automatic) as the drivers of behavior. It has been widely used as a theoretical framework for development and evaluation of health services interventions. TAM is a widely used information systems theory that models how users come to accept and use a technology. Using COM-B, the interview guide will explore perceived barriers and facilitators that could influence stakeholders' willingness to continue implementation beyond the study period. (See *Attachment A* below for the proposed interview guide; note this is subject to modifications at the discretion of the research team as it is put into use).

**Satisfaction and usability:** Through the semi-structured interview, we will determine the Net Promoter Score (NPS) as a quantitative measure of user satisfaction and willingness to use. The NPS is based on a single question: *How likely is it that you would recommend our service to a friend or colleague?* This score is increasingly used in health services research as a summary of consumer satisfaction.

Since implementation of the program includes use of an online digital guide, we will use the TAM framework to examine the usability of the digital guide and report the TAM score (overall and for each theoretical variable) as a quantitative measure of usability. The theoretical variables comprising the TAM

score include Perceived Usefulness (PU), Perceived Ease of Use (PEU), perceived facilitators, and intention to use.

**Survey analysis:** We will use summary statistics to describe the Net Promoter Score and TAM score (overall and for each variable) by study arm (full-support vs self-guided) and by type of stakeholder (site champion vs practice change facilitators vs physician lead).

**Qualitative analysis:** Qualitative analysis of interview transcripts will examine barriers and facilitators to implementation of MAP BP from the perspective of local stakeholders. Transcripts will be coded using an integrated inductive-deductive qualitative data analysis approach. In particular, we will use the constant comparison method, an inductive qualitative data analysis approach in which data are broken down, compared for similarities and differences, and grouped together under similar conceptual themes to uncover a wide variety of themes from the data, while also employing predetermined conceptual codes drawn from COM-B and TAM. One study author, blinded to randomization assignments, will independently code the transcripts (TBD) to identify preliminary themes through initial readings of the transcripts. Iterative discussions among all the study investigators will refine thematic categories and lead to a final set of salient themes identified across all the interviewees.

**Table 1. Using the capability, opportunity, motivation and behavior (COM-B) framework to assess barriers and facilitators to implementation of both versions of the MAP BP program (self-guided and full-support)**

COM-B domains	Definitions	Proposed interview/survey question areas
1. Capability - Psychological (Knowledge, memory, cognitive and interpersonal skills, decision-making skills, behavioral regulation, etc.) - Physical	Stakeholders' perceived ability to use the MAP BP program and its tools to successfully affect practice change in their clinic to improve BP control  Capacity of clinic(s) personnel (medical assistants, nurse, primary care providers) to implement best practices recommended in MAP BP – e.g., use of treatment algorithm, BP measurement protocol.	1. Do you believe the MAPBP training and tools have enabled you and your team to favorably affect practice for HTN management at your clinic(s)? Why/why not? Barriers/Facilitators?  2. How much do you agree that the MAP BP program improved the capacity of your clinical staff to better measure, treat, and manage hypertension? Please explain.
2. Opportunity a. Physical : environmental context and resources b. Social : social influences	Factors (organizational, technology, or cultural infrastructure) at the clinic or health system that makes adoption/implementation of MAP BP easy or difficult  Capacity of the clinic(s) to implement best practices recommended in MAP BP – e.g. frequent patient encounters, use of treatment algorithm, BP measurement protocol.	1. What were your most significant challenges in implementing MAP BP in your clinical environment?  2. How supportive were your clinic(s) leaders, doctors, nurses, and staff of the program? (E.g. BP measurement protocol, treatment intensification algorithm, etc.)  3. Describe aspects of your clinical environment (personnel, resources, and technology) that made it easier or harder to implement MAP BP?
3. Motivation a. Automatic : Emotion b. Reflective : Intentions, beliefs about capabilities, beliefs about consequences	Stakeholders' reported level of value placed on management of hypertension  Stakeholders' reported likelihood they will continue to use MAP BP tools and continue to lead practice change for hypertension management	1. Considering all the priorities that comes with your role, how important is improving your clinic(s)' BP control?  2. How much do you agree that your clinic now sees patients with uncontrolled BP more frequently and providers treat uncontrolled BP more aggressively? Please explain.  3. Will you continue to use MAP BP tools and training going forward? Why/why not? How?
4. Behavior	Stakeholder choices in implementing the MAP program, changes made in the clinical environment, and steps taken to ensure fidelity to various components of the intervention.	1. Did your clinic(s) choose a hypertension treatment algorithm? Which one?  2. Did your clinic(s) train providers on the algorithm? If so, how?  3. How did your clinic(s) choose to disseminate the algorithm? (e.g. posters, pocket cards, pdf attachment in EHR, electronic decision support tool)

Table 2. Usability measures informed by the Technology Acceptance Model (TAM) and corresponding COM-B domains to assess usability of the online digital guide for the MAP program.		
TAM usability Measures	Definitions	COM-B
1. Perceived usefulness and satisfaction	Level of agreement that they were satisfied with the digital guide and that it added value to their work or was helpful in enhancing their ability to implement the three components of the MAP program	Reflective motivation
2. Ease of use	Level of agreement that the digital guide is easy to use and is useful, for facilitating practice change in hypertension management.	Psychological capability
3. Adoption and intention to use	Level of agreement they will continue to use and/or would recommend colleagues to use it to implement systems changes for hypertension management	Behavior and Motivation

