#### **B. Barriers and Facilitators to Implementing BP MAP**

1. Let's start by talking about your **EXPERIENCES** using the BP MAP **DIGITAL GUIDE**.

- a. What aspects of the **DIGITAL GUIDE** were **HELPFUL** to you and your clinical teams when implementing BP MAP? (**Probe:** How were they helpful? Can you explain?)

- i. *[After each response]:* What else about the **DIGITAL GUIDE** did you find helpful?
  - b. In what ways do you think the BP MAP **DIGITAL GUIDE** could be **IMPROVED** to help you and your clinical teams implement BP MAP? (**Probe:** Is there something about the **DIGITAL GUIDE** that could be added or made better to help you and your clinical teams implement BP MAP best practices?)
    - i. *[After each response]:* What else about the **DIGITAL GUIDE** do you think could be improved?
2. Next let's talk about the **AMA Facilitator** that worked with you and your team to support implementation of BP MAP.
  - a. What things did the **AMA Facilitator** do that you found **HELPFUL** when implementing BP MAP? (**Probe:** In what ways did the **AMA** make it **EASIER** for you to implement BP MAP?)
    - i. *[After each response]:* Is there anything else that the **AMA FACILITATOR** did that you found **HELPFUL** or **USEFUL** when implementing BP MAP?
  - b. What could the **AMA** do **MORE OF** or **DO DIFFERENTLY** to help you implement BP MAP? (**Probe:** Is there something you think could be added to the role of the **AMA** to help you implement the BP MAP program?)
    - i. *[After each response]:* Is there anything else that the **AMA FACILITATOR** could do **MORE OF** or **DO DIFFERENTLY** to help you implement BP MAP?
  - c. Was there anything that the **AMA FACILITATOR** did during your interactions that was **NOT HELPFUL**? (**Probe:** Is there anything that the **AMA FACILITATOR** did that you think should be avoided?)

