### **C. Changes Made in the Clinical Environment**

1. Let's change topics. Now I would like to talk to you about the changes made in the processes and procedures at your clinic as a result of implementing BP MAP.
  - a. Tell me about any changes that were made at your clinic(s) related to how staff **MEASURE BLOOD PRESSURE**. (**Probe:** Did your clinics change anything about the type of equipment used or the process used to prepare or position the patient when measuring their blood pressure? Any other changes such as adding a chair for patients to sit on, or moving the BP wall device to eye level?)
    - i. *[After each response]:* Describe for me how do you think [insert response] has led to improved blood pressure control in the patients at your clinic(s)?
    - ii. *[After each response]:* What other changes were made at your clinic(s) regarding how your team measures blood pressure?

- b. What changes were made at your clinic(s) regarding the way clinicians **CHANGE THE DOSE OR TYPE OF MEDICATION** prescribed for patients with hypertension to help improve their blood pressure control. (**Probe:** Did your clinics implement any best practices change anything about how they decide when to intensity or change medications for patients with high blood pressure?)
    - i. *[After each response]:* Describe for me how do you think [insert response] has led to improved blood pressure control in the patients at your clinic?
    - ii. *[After each response]:* Do you know of anything else done differently when deciding when to change medications for patients with hypertension?
  - c. Talk to me about any **CHANGES** that were made at your clinics in the way you use **DATA** to better understand and improve blood pressure control rates in your patients. (**Probe:** Did your clinics implement any BP MAP components focused on using data in new ways?)
    - i. *[After each response]:* Describe for me how do you think [insert response] has led to improved blood pressure control in the patients at your clinic?
    - ii. *[After each response]:* Is there anything else that you now do differently with data to help staff in your clinic improve hypertension control rates?

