#### **E. Overall Thoughts and Moving Forward**

We are almost finished, I just have one last question for you. As we finish up, I'd like for you to think back on all that your clinic changed as a result of implementing BP MAP. Think about the practices and procedures

- a. What do you feel were the **MOST SIGNIFICANT CHANGES** that occurred in your clinics that resulted from implementing BP MAP? (**Probe:** What were the most impactful changes in the clinical workflows or practices that enhanced the way clinics manage hypertension?)

We sincerely appreciate your time today. Your input has been so valuable for the BP Map Program.

Are you interested in receiving the Amazon Gift Card for your time today? \_\_\_\_\_ Yes \_\_\_\_\_ No

Please provide me with the email you would like it to be sent to:

---

INTERNAL USE ONLY:

Date Gift Card Was Sent: \_\_\_\_\_

Order Number: \_\_\_\_\_

Person Sending Gift Card: \_\_\_\_\_

Participant Name: \_\_\_\_\_ Study Site: \_\_\_\_\_

Interview Date: \_\_\_\_\_ Interview Time: \_\_\_\_\_

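### The attached interview guides ask nothing about continuing the program, presume that BP control improved, and leave unsettled which instrument carries the Net Promoter Score

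*Combined protocol and SAP*

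**What the plan says.** The Limited program evaluation section gives sustainability as its objective and describes two instruments: a 10-minute online survey and a 60-minute virtual exit interview. Stakeholders who have not done the survey beforehand complete it at the start of the interview session.

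- **Interview guide paragraph.** The guide is to examine how feasible it is to keep both versions of the program running. The paragraph adds that "the interview guide will explore perceived barriers and facilitators that could influence stakeholders' willingness to continue implementation beyond the study period". It calls the attached guide proposed and open to modification.
- **Satisfaction and usability paragraph.** "Through the semi-structured interview, we will determine the Net Promoter Score (NPS) as a quantitative measure of user satisfaction and willingness to use". The score rests on one item: "How likely is it that you would recommend our service to a friend or colleague".
- **Survey analysis paragraph.** "We will use summary statistics to describe the Net Promoter Score and TAM score", by study arm and by type of stakeholder.
- **Table 1, Motivation row.** A drafted question reads "Will you continue to use MAP BP tools and training going forward", with follow-ups on why and how. The column heading covers interview and survey together.
- **Attachment A.** It holds two guides, both for Site Champions, one per arm. The closing section of each, headed Overall Thoughts and Moving Forward, opens "We are almost finished, I just have one last question for you". The question that follows concerns the most significant changes that occurred. After each change reported in the section on the clinical environment, the interviewer says, in the Full Support guide, "Describe for me how do you think [insert response] has led to improved blood pressure control in the patients at your clinic(s". The Self-Guided guide uses the same probe for a single clinic.

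**The concern.** An exit interview happens once per stakeholder, so a question left out may not be recoverable. If the guides are used as attached, the instrument to which the plan gives the sustainability aim does not ask respondents whether they will continue, or what would help or prevent it.

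The probe raises a separate problem. Whether BP control improves, and by how much in each arm, is what the trial tests. The sample size paragraph assumes negligible change in the Self-Guided arm. A probe that takes improvement as given invites a success story from every clinic, including those where control did not move, and the coded themes would carry that slant.

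The Net Promoter Score is one of the evaluation's two named quantitative measures. If the interview team believes the survey holds the item while the survey team believes the interview does, it could be missed or asked twice.

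**Working it through.** No sample size, alpha or event figure bears on this point. The check is a reading of both guides in full against what the Limited program evaluation section promises.

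**1. Continuation**
- Promise: the guide examines the feasibility of continuing, and explores what could influence willingness to do so after the study.
- Full Support guide, sections B to E: experience with the digital guide and the AMA Facilitator, changes made, what made implementation easier or harder, and most significant changes. All of it looks back, apart from requests for improvements to the guide and to AMA support.
- Self-Guided guide, sections F to I: the same pattern, with the kick-off webinar in place of the facilitator.
- Count of questions on continuing the program: 0 in Full Support + 0 in Self-Guided = 0 of 2 guides.
- Table 1 already contains suitable wording, so the content was planned but did not reach the guides.

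**2. Probe that presumes benefit**
- Each guide has four change topics: measuring BP, changing medication, using data, and working with patients.
- The probe follows every topic in both guides: 4 × 2 = 8 places.
- No version in either guide leaves room for the answer that a change had no effect.

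**3. Net Promoter Score**
- Collection: the interview, according to Satisfaction and usability.
- Analysis: alongside the TAM score, under Survey analysis.
- Recommendation items in the guides: 0 of 2.
- If the interview is the source, the guides omit the item. If the survey is the source, the Satisfaction and usability paragraph names the wrong instrument. The two paragraphs and the attachment cannot all stand as written.

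**4. Facilitator label**
- The Interventions section describes a Practice Change Facilitator who leads Full Support, supported by an AMA Improvement Advisor.
- Section B of the Full Support guide asks three questions about an AMA Facilitator "that worked with you and your team to support implementation of BP MAP". The protocol body defines no role by that name.
- This is a mismatch of labels. The evaluation section lists Practice Change Facilitators as interviewees and nowhere undertakes to measure them.

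**The case against.** The strongest reply is that the guides are only half of the data collection.

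- **Survey.** Its items are not in the documents. It may be completed within the interview session, Table 1 covers interview and survey areas together, and the score is analysed as survey data. Table 2 also includes intention to keep using, or to recommend to colleagues, the digital guide. This reply stands to a point: it blocks any claim that the information will go uncollected. It does not answer the plan's own statements about the interview and its guide, and Table 2 concerns the digital guide, not the program.
- **Barriers and facilitators.** The sentence on willingness promises to explore barriers and facilitators, and the guides do so at length. That is fair, but those questions concern past implementation, and the plan separately says the guide examines the feasibility of continuing.
- **Probe.** It follows an open question about any changes, after an introduction saying that no answer is right or wrong. Both guides ask about difficulties, and the Full Support guide asks what was unhelpful. This softens the slant without removing the presumption from the wording.
- **Draft status.** The guides are proposed and can be changed. That makes correction easy but does not make the attachment agree with the text.

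A reader might infer that Full Support's key component goes unexamined because the Practice Change Facilitator is not named. The documents do not support that. The inclusion criteria for Active Clinics allow the Site Champion being interviewed to hold that role, Practice Change Facilitators are themselves to be interviewed, and the guide asks whether someone or something helped.

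**Conclusion.** The point holds in limited form, as a worthwhile minor improvement. Three things are established from the text: no continuation question in either attached guide (0 of 2), eight probes that presume improved BP control, and a Net Promoter Score assigned to the interview, analysed as survey data and absent from both guides.

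A reader might go further and conclude that the study will have no Net Promoter Score by arm, or no account of willingness to continue. Neither follows, because the survey has not been seen and may carry both.

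The finding covers only the two Site Champion guides supplied and assumes that their text is complete. Nothing can be said about instruments for physician leads or Practice Change Facilitators. The effect is confined to the limited program evaluation. The primary outcome, the three hypothesis tests and the power calculation are untouched.

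**What to change.** 1. Add the Table 1 question, "Will you continue to use MAP BP tools and training going forward", with its follow-ups on why and how, to the closing section of both guides.
2. Reword the probe in all eight places to neutral form, for example: *What effect, if any, did [response] have on blood pressure control at your clinic?*
3. Reconcile Satisfaction and usability with Survey analysis by naming the one instrument that carries the Net Promoter Score, and confirm that the item is in it. State the response scale at the same time, since the plan gives none.
4. Optionally, align the AMA Facilitator label in the Full Support guide with the roles defined under Interventions.

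The cost is an edit to an attachment that the plan already allows to be modified, plus a few minutes in a 60-minute interview. If the survey already asks about continuation, the interview question overlaps with it but still adds the reasons in the respondent's own words.
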